5.5 Pregnancy restriction

No studies have been conducted on possible side effects of ABSK061 in fetuses or infants. Participants may not participate in this study if they are preparing for pregnancy. Male or female participants of childbearing potential who decide to participate in this study must agree to use appropriate contraception from the time of signing the informed consent form until 6 months after the last dose of the investigational product. Appropriate contraceptive measures include vasectomy (male sterilization), use of condoms, use of contraceptive membranes with spermicidal gel (Pure), contraceptive rings, and surgical birth control.

If a participant 's partner becomes pregnant at any time during the study, or if the participant believes that her partner may become pregnant, the study doctor must be notified immediately.

6 Investigational Medicinal Products, Medication History and Concomitant Medications

6.1 Physical Properties of Investigational Product

The chemical name of this compound (ABSK061-NX) 3- (2,6-dichloro-3,5-dimethoxyphenyl) -1-methyl-7- (1- (2-morpholinethyl) -1H-pyrazol-4-yl) -1,6-naphthyridin-2 (1H) -one is the free base form of ABSK061.

The formulations provided in this study were ABSK061 capsules in the strengths of 0.2 mg/capsule and 5 mg/capsule, the 0.2 mg strength capsule contained 4 ABSK061 micro-tablets containing 0.05 mg active ingredient, and the 5-mg capsule contained 10 ABSK061 micro-tablets containing 0.5 mg active ingredient. Each tablet contains the following inactive pharmaceutical excipients: microcrystalline cellulose, mannitol, croscarmellose sodium, colloidal silicon dioxide, magnesium stearate, film-coating premix (gastric soluble, where the 0.05 mg microt film-coating premix is pink and the 0.5 mg microt film-coating premix is white).

6.2 Labeling of Investigational Product

The label of the investigational product will include the sponsor name, protocol number, drug name, drug dosage form, drug batch number, dosage unit, dosage and administration, duration of use, storage conditions, etc., and indicate that the drug is "for clinical trial use only". The labeling of the investigational medicinal product will contain information that complies with applicable regulatory requirements. The investigational product may not be relabeled without prior approval from the sponsor.

In addition, the labeling or labeling of the investigational product should be in accordance with local and national regulations and will not in any way carry any false or misleading statement and will not indicate that the investigational product is safe or effective for the purposes of the study.

6.3 Packaging and Storage of Investigational Medicinal Products

The shells used for the ABSK061 microt are empty hydroxypropylmethylcellulose capsules (Vcaps Plus 0 #, white opaque cap/white opaque body, Sprinkle). The packaging

materials used for microspheres in ABSK061 capsules are high-density polyethylene (HDPE) bottles for oral solid pharmaceutical use, polyolefin functional combination caps for oral solid pharmaceutical use, and high-density polyethylene desiccant tank (1 g/tank) for oral solid pharmaceutical use. Packed in 75 mL HDPE bottle in 30 capsules per bottle, 1 canister of desiccant.

The investigational product should be stored in accordance with the relevant requirements in the drug label.

6.4 Management, Dispensing and Recovery of Investigational Medicinal Products

The investigator is responsible for the investigational product at the study site. The investigator should ensure that the investigational product is used in compliance with protocol requirements. The investigator may designate a pharmacist or other appropriate person to be responsible for drug management and dispensing. The warehousing information, inventory quantity, distribution, return to the sponsor (or destruction after approval by the sponsor) of the investigational product should be fully documented and kept at the study site. These records will be used to demonstrate that the participant has obtained sufficient investigational product from the sponsor to be administered at the dose specified in the protocol. Drug records will include date, quantity, batch/serial number, expiration time (if applicable), and participant number. Records will be reconciled by the sponsor or its designee at the time of monitoring, and the sponsor must be notified immediately if a dispensing error or record mismatch is found. All used and unused investigational product (s) should be retained at the study site until the monitor accountability is completed or the sponsor authorizes destruction. All unused or expired investigational products should be returned to the sponsor or its designated third party, or destroyed and documented with the authorization of the sponsor. The relevant procedures of drug application, distribution, storage, accountability and destruction are detailed in the Investigational Drug Management Manual.

6.5 Prior Medications and Concomitant Therapies

Medications that ended 14 days prior to the first dose of ABSK061 to the end before the first dose of ABSK061 were considered prior medications. Medications taken from the first dose of ABSK061 to 7 days after the last dose were considered concomitant medications in the single-dose PK study of Part I and the soft food co-administration study in Part III. In the MAD study of Part II, medications taken from the first dose of ABSK061 to 14 days after the last dose were considered concomitant medications. Any other medication other than the protocol is prohibited from 14 days prior to the first dose until the entire study unless an AE requiring treatment or other sudden illness (including viral respiratory tract infections such as COVID-19) occurs. If treatment of an AE or other disease is required, the investigator is encouraged to discuss it with the sponsor or the clinical study doctor. Any medication considered necessary for the safety and health of the participant may be administered at the discretion of the investigator and documented in the study medical record. All medications (except study drug) and important non-drug therapies received by the participant during the study must be recorded.

7 Study Procedures

7.1 Study flow

Refer to Table 4 Part I study plan, Table 5 Part II study plan, and Table 6 Part III study plan for specific study procedures. Of these, the study schedule describes the contents and specific times of each study plan throughout the study flow, and the sampling schedule describes the time of PK sample collection. Participants may be asked by the investigator to perform additional safety assessments to determine the relationship between the occurrence or duration of the clinical event and the investigational product, as required by clinical practice.

7.2 Participant Registration and Randomization

Participants will be strictly screened and assessed by the investigator. Once the participant's eligibility for participation in the clinical study is confirmed, the investigator or his/her designated study personnel will complete the participant registration form.

After signing a written informed compassionate letter and completing the necessary screening assessments, participants in Parts I and III were assigned to different study sequences according to randomization codes and Part II participants entered different study sequences according to the enrollment number. If a participant withdraws from the study, his/her screening number, randomization number, or enrollment number will not be reused. No participant will be enrolled or initiated with the investigational product until the screening number is registered and assigned.

Assignment of Screening Number

The entire study will consist of three study parts, and participants who sign the informed consent form will be assigned a unique screening number in the format of "S+3 digit sequential number" in the chronological order of signing the informed consent form. For example: screening number S001 represents the first informed consenting participant at the study site, screening number S002 represents the second informed consenting participant at the study site, and so on.

Assignment of Enrollment Number

Participants who are screened successfully in Part II will be sequentially assigned enrollment numbers in the order of screening numbers in the format of "2000 + 3 digits", e.g., enrollment number 2001 indicates the first participant who has successfully entered Part II according to the order of screening numbers, enrollment number 2002 indicates the second participant who has successfully been screened into Part II according to the order of screening numbers, and so on.

Randomization Number Assignment

Part I: participants screened successfully (i.e. those who meet the inclusion criteria and do not meet the exclusion criteria after screening) will be randomized in A 1: 1: 1 ratio to Sequences A, B, and C. According to the Randomization Plan and/or the Randomization Coding Form (provided by Shanghai Hezhui Biopharmaceutical Technology Co., Ltd.), participants will sequentially assign randomization numbers according to the order of screening numbers. Based on the setting of sample size in this protocol, the proposed range of randomization number is: 1001 ~ 1018.

Part III: participants screened successfully (i.e. participants who meet the inclusion criteria

and do not meet the exclusion criteria after screening) will be randomized in a 1: 1: 1 ratio to Sequence F, Sequence G, or Sequence H. According to the Randomization Plan and/or the Randomization Coding Form (provided by Shanghai Hezhui Biopharmaceutical Technology Co., Ltd.), participants will sequentially assign randomization numbers according to the order of screening numbers. Based on the setting of sample size in this protocol, the proposed range of randomization number is: 3001-3012.

Participant Replacement

Participants who have been randomized to Part I and Part III but fail to receive the first dose for any reason will be replaced and the replacement participant will be consistent with the study sequence of the replaced participant. The random number of the replacement participant will be the random number of the replaced participant plus 100. For example, a participant with a random number of 1001 will be replaced with 1101, a participant with a random number of 3002 will be replaced with 3102, and so on.

Participants who have been assigned an enrollment number to Part II but fail to receive the first dose for any reason will be replaced and the replacement participant will be consistent with the study sequence of the replaced participant. The replacement participant enrollment number will be the replacement participant enrollment number plus 100. For example, a participant with an enrollment number of 2001 will be replaced with 2101, and so on.

Participants who have been dosed are not allowed to be replaced.

7.3 **Blinding**

This study is an open-label study.

7.4 Screening failure

Participants who have signed informed consent but fail to start dosing for any reason will be considered screening failures. The reason for failure to start dosing will be entered in the Screening Inclusion Form and recorded on the eCRF as required by the eCRF completion guidelines.

7.5 Investigational Product Assignment

Part I: participants were screened to meet eligibility criteria and were randomized 1: 1: 1 to receive A single microchip dose of 1 mg, 10 mg, and 35 mg of ABSK061 in Sequences A to C, respectively.

Part II: participants in Sequence D received once daily oral administration of 5 mg ABSK061 microchips for 4 consecutive days; participants in Sequence E received once daily oral administration of 20 mg ABSK061 microchips for 4 consecutive days.

Part III: after screening and meeting the eligibility criteria, participants were randomly assigned 1: 1: 1 to Sequences F, G, and H to receive Treatment 1 (5 mg ABSK061 microchip fasted), Treatment 2 (5 mg oral ABSK061 microchips sprinkled on a spoon of yogurt under fasting conditions), and Treatment 3 (5 mg ABSK061 microchip was sprinkled on a spoon of applesauce under fasted state). Wherein, participants in Sequence F will receive Treatment 1, Treatment 2, and Treatment 3 in the morning on D1 of Cycle 1 Day 1, D4 on Day 1 of Cycle 2, and D7 on Day 1 of Cycle 3, respectively; participants in Sequence G will receive Treatment 2, Treatment 3, and Treatment 1, respectively, on Cycle 1 Day 1 D1, Cycle 2 Day 1 D4, and

Cycle 3 Day 1 D7 in the morning; participants in Sequence H will receive Treatment 3, Treatment 1, and Treatment 2 in the morning on Cycle 1 Day 1 D1, Cycle 2 Day 1 D4, and Cycle 3 Day 1 D7, respectively.

7.6 Investigational Product Administration

The drug was administered under fasting conditions. All participants were fasted overnight for at least 10 hours before dosing, drinking water was prohibited from 1 hour before dosing to 1 hour after dosing, and no food was allowed for 4 hours after dosing. The investigational product must be swallowed completely and cannot be chewed. When the number of microchips is large, dosing may be divided into multiple doses, but participants must complete swallowing of all microchips at the prescribed dose within 3 minutes.

After removal of the ABSK061 capsules, open the cap and pour out the corresponding number of microt: 5 0.2 mg capsules for 1 mg ABSK061, 10 microt for 5 mg ABSK061, 2 5 mg capsules for 10 mg ABSK061, 4 5 mg capsules for 20 mg ABSK061, and 70 microt for 7 5 mg 35 mg ABSK061.

Part I & II: all participants received the corresponding number of microchips directly with 180 mL of water.

Part III: participants receiving Treatment 1 took 10 0.5 mg tablets directly with 180 mL of water; participants receiving Treatment 2 dispersed 10 0.5 mg tablets on 1 tablespoon of yogurt (approximately 15 mL) and swallowed together, followed by 180 mL of water immediately; participants receiving Treatment 3 sprinkled 10 0.5 mg tablets on 1 tablespoon of applesauce (approximately 15 mL) and swallowed them together, followed by 180 mL of water immediately.

7.7 Study Duration

Including screening period (and baseline period), trial period and safety observation period/follow-up period.

Screening + Baseline: 14 days.

Part I: the single dose PK study consisted of a single dose (1 day) and a safety observation period (7 days).

Part II: the multiple-dose escalation PK study included multiple doses (4 days) and a safety observation period (14 days).

Part III consists of three cycles (3 days per cycle for a total of 9 days) and a safety observation period (7 days). Whether or not a participant completing the current period of the study enters the next cycle of the study will be determined comprehensively by the investigator based on the participant's physical condition and relevant visit examination results.

For participants who interrupt or permanently discontinue the study due to an adverse event or clinically significant laboratory abnormality, the frequency of visits will be determined comprehensively as required by the Testing Facility or as clinically indicated until the AE resolves or stabilizes, whichever occurs first.

7.8 Study Compliance

Dosing will be performed under the supervision of the investigator. After administration, the investigator must examine the oral cavity of the participant to ensure that the investigational

product can be swallowed completely and correctly.

7.9 Dose Modification

No dose modifications were allowed during this study.

7.10 Participants lost to follow-up

A participant will be considered lost to follow-up if he/she fails to return for a visit examination multiple times at the scheduled visit time and the site is unable to contact the participant or the participant explicitly refuses to follow-up. The specific criteria for not being able to contact are: telephone calls twice daily (morning and afternoon), unconnected/hung up/shutdown/shutdown/empty for three consecutive days, which will be recorded as lost to follow-up, each time by the notifier.

7.11 Participant Withdrawal

Participants may withdraw voluntarily from the trial at any time without giving reasons and without any penalty or discrimination. The investigator may also ask the participant to withdraw from the study based on the actual clinical situation of the participant. Reasons for discontinuation or withdrawal from the study may include:

- Adverse events:
- Death:
- Protocol violation;
- Lost to follow-up;
- Withdrawal of consent by participants;
- Pregnancy
- Study termination by the sponsor;
- Participants were considered unsuitable for participation in the study by the investigator.

If a participant experiences vomiting within 2 hours of dosing, the investigator may determine whether the participant needs to withdraw from the study early based on the severity of vomiting.

If a participant voluntarily withdraws from the study, an attempt should be made to contact the participant to determine the reason for discontinuation. For any reason, premature withdrawal should complete all study procedures and assessments required for "early withdrawal". All participants who interrupt the study due to an AE will be followed until the AE resolves or stabilizes, as detailed in 8.3.13 Safety Reporting Period.

7.12 Early termination of the study

The investigator or sponsor may choose to terminate the study prematurely if he/she believes there is sufficient reasonable cause. The party discontinuing the study will provide written notice to the investigator or sponsor stating the reason for discontinuation of the study.

7.12.1 Criteria for Study Suspension or Early Termination

Criteria for study suspension or early termination include:

- 1. New information on the safety of the investigational product indicates a change in the pre-existing risk profile of the investigational medicinal product, resulting in an unacceptable risk to participants participating in the study.
- 2. A serious GCP violation occurred that seriously affected the achievement of the primary study objectives or jeopardized the safety of participants.
- 3. The sponsor may suspend or prematurely discontinue the study for reasons unrelated to the study process.

7.12.2 Criteria for Site Suspension or Early Termination

If a site (including the investigator) is found to be in serious violation of GCP, protocol, contractual agreements, or is unable to ensure the proper conduct of the study, the site may be suspended or prematurely terminated.

7.12.3 Procedures for Suspension or Early Termination of the Study

If the sponsor chooses to suspend or terminate the study itself or a study center, the sponsor will provide instructions for specific procedures for study suspension or early termination; during the suspension or termination of the study, applicable sites will follow this procedure for subsequent operations.

7.13 End of study

A participant is considered to have completed the study if he/she has completed all visits to the study, including the last visit or last trial procedure shown in the flowchart. The end of study was defined as the completion of all procedures in the last visit or flowchart for the last participant (including safety telephone follow-up).

8 Study Assessments

8.1 Pharmacokinetic assessment

8.1.1 PK blood sampling

PK blood samples should be collected according to Table 7 Part I PK sampling times, Table 8 Part II PK sampling times, and Table 9 Part III PK sampling times, and plasma samples of all participants in this study before and after dosing to determine the concentrations of ABSK061 and its metabolites (if applicable) for PK assessment. The actual date and time of each sampling (24-hour clock) will be recorded. The consumables used for blood sample collection are provided in the Laboratory Manual.

8.1.2 Sample analysis

Approximately 2 mL of venous blood samples will be collected at each sampling time point to determine plasma concentrations of ABSK061 and its potential high proportion of metabolites, if applicable.

8.1.3 Sample Handling, Storage and Shipment

PK samples will be analyzed at a central laboratory and plasma sample processing, storage,

labeling, and shipping details will be referenced in a separate laboratory manual.

8.1.4 PK Parameter Analysis

The PK parameters of ABSK061 for each participant under different dosing conditions will be calculated and subjected to descriptive statistical analysis based on individual pharmacokinetic time-concentration profiles and actual sampling times.

The following PK parameters will be reported. Additional PK parameters will be reported if needed.

	Parameters	Definition		
Single dose	tmax	Time to peak, i.e. the actual sampling time to reach the peak concentration		
	Cmax	Peak concentration, i.e. observed peak concentration		
	tlast	Actual time of last quantifiable observed concentration (non-BQL)		
	AUClast	Area under the ABSK061 plasma concentration-time curve from 0 to the last measurable (non-BQL) concentration time point (calculated using the Linear Up Log Down trapezoidal method)		
	AUC0-∞	The area under the ABSK061 drug concentration-time curve from time 0 to infinity was calculated as follows: AUC0- ∞ = AUClast + Clast/ λz ; Clast refers to the actual last measurable (non-BQL) plasma concentration of ABSK061.		
	kel	Terminal elimination rate constant, calculated by linear regression after logarithmic transformation from the end of the drug concentration-time curve.		
	t1/2	Apparent elimination half-life, calculated as follows: $t1/2$, $\lambda = \ln 2/\lambda z$,		
	CL/F	Total apparent clearance of drug after single oral administration: CL/F = Dose/AUC0- ∞		
	Vz/F	Apparent volume of distribution of the drug after single oral administration: $Vz/F = Dose/(AUC0-\infty \cdot \lambda z)$		
Multiple dose	tmax,ss	Actual time of maximum observed concentration during the dosing interact steady state		
	Cmax,ss	Maximum concentration during the dosing interval at steady state		
	Cmin,ss	Trough concentrations over the dosing interval at steady state		
	AUCtau,ss	Area of the concentration-time curve over the dosing interval at steady state		
	ARAUC	Accumulation index based on AUC calculation as follows: ARAUC AUCtau, ss/AUCtau, sd		
	ARCmax	When AUC is not available, the accumulation index will be calculated as Cmax instead of AUC. The accumulation index based on Cmax was calculated as follows: ARcmax = Cmax, ss/Cmax, sd		
	t1/2,eff	Effective half-life, calculated as follows: $t1/2$, eff = Ln (2) * tau/Ln ((AR/(AR-1))), where AR is ARAUC		
	CLss/F	CLss/F = Dose/AUCtau,ss		

Table 10 PK parameters and their calculations

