of which 33 patients had evaluable PK data: ABSK061 was rapidly absorbed after a single dose, with a median tmax interval of 0.5 to 1.5 hours across dose groups; the mean terminal t1/2 values for each dose group ranged from 2.9 to 6.8 hours. The apparent volume of distribution of ABSK061 after oral administration ranged from 93 to 136 L, suggesting extensive distribution in vivo. No significant accumulation was observed after multiple doses, with mean accumulation ratios of 1.2 to 2.2 for AUC across dose groups following QD or BID dosing. The inter-individual differences among ABSK061 participants were small, with coefficients of variation of 20% to 43% and 5% to 42% for Cmax, ss and AUCtau, ss, respectively, after multiple doses.

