The Part II Multiple Dose Escalation (MAD) study will evaluate the safety and tolerability of ABSK061 at this dose by conducting repeat dose trials of 5 mg and 20 mg successively based on the results of the single dose study. The placebo group will not be included in this study. Since most ABSK061-related TEAEs in ABSK061-101 are abnormalities such as laboratory tests and ophthalmic examinations, relevant monitoring items have been included in this study as the primary and objective evaluation indicators of safety, and whether the placebo group is set up will not have an impact on objective results such as laboratory parameters and PK. The trial was small in size and limited in sample size, and the addition of placebo significantly reduced the efficiency of the trial. Based on the half-life (median 5.4 h in adult oncology patients) and dosing frequency (QD) of the study drug, it can be stable after approximately 3.3 consecutive days of dosing, so it is proposed to test steady-state PK after 4 consecutive days of dosing in this MAD trial. Finally, the safety observation period for this MAD study is proposed to be 14 days due to the short half-life of the investigational drug, which can be completely eluted from the body within 3 days.

The PK of 5 mg ABSK061 was performed in Part III and the effect on the PK of the investigational drug at this dose when the microchip was taken with soft food, since dysphagia may still be present in young children, and 5 mg fell within the effective dose interval for children with ACH at that age based on the estimated effective dose. Common pure yogurt and applesauce 2,3 will be used in this study as soft foods to help swallow. Participants in the control group took the tablets directly with 180 mL of water, and participants in the test group were required to take 180 mL of water immediately after helping swallow the tablets with yogurt or applesauce to evaluate the effect of a soft meal on PK. A washout period of 3 days (more than 7 half-lives) was set between the two doses of the participants, minimizing the potential carryover of the study drug in the previous cycle. The last blood sampling point 48 h after administration also covers 7 half-lives, which can ensure the AUC0-∞ of the extrapolated drug.

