9.1 Sample Size Estimation

The objective of this study was to evaluate the PK profile of ABSK061 capsules in single or multiple oral doses, to assess the effect of soft food on the pharmacokinetics of ABSK061, and to explore the dose-exposure proportionality of ABSK061 microt. The sample size was estimated based on actual considerations and feasibility, and no hypothesis testing was performed.

The study was planned to enroll 18 participants in Part I and to be randomized in A 1: 1: 1 ratio to three different study sequences, A, B, and C.

Part II plans to enroll 12 participants and preset 2 study sequences (sequences D and E, 6/sequence).

Part III planned to enroll 12 participants and were randomized in a 1: 1: 1 ratio to three different study sequences: F, G, and H. Based on the data from the Phase 1 trial in patients with solid tumors of ABSK061-101, the weighted mean of the geometric coefficient of variation (CVw%) of each dose group was obtained for AUC0-∞, AUClast and Cmax. Considering that this was the inter-patient coefficient of variation, the intra-individual coefficient of variation (CVw%) in healthy participants in this study was estimated as 70% of the above-mentioned weighted mean, I.e. 27.272%, 27.384%, 21.966%. Although the sample size for this trial is not based on statistical testing, as a reference, it is assumed that there is no difference between the drug taken with water and with soft food. The two-sided 90% confidence intervals for the estimated precision (90% confidence interval half-width) and the Ratio of the Geometric Means Ratio (GMR) of the log-transformed PK parameters (taken with soft food-water) at different sample sizes are presented below.

Table of Estimated Accuracy of Primary PK Parameters at Different Sample Sizes (GMR =

1)

Part III							
Three-	AUC0-∞		AUClast		Cmax		
sequence,							
three-period	AU	€0-∞	AU	AUCIASI		Ciliax	
crossover							
design							
Evaluable Participants	Accuracy	GMR	Accuracy	GMR	Accuracy	GMR	
		90%		90%		90%	
		confidence		confidence		confidence	
		interval		interval		interval	
9		0.801,		0.800,		0.835,	
	0.222	1.249	0.223	1.250	0.180	1.198	
12		0.828,		0.828,		0.858,	
	0.189	1.208	0.189	1.208	0.153	1.165	
15		0.846,		0.846,		0.874,	
	0.167	1.182	0.167	1.182	0.135	1.145	

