9.3.5 PK Data Analysis

ABSK061 pharmacokinetic parameters will be calculated and analyzed by a standard noncompartmental model. The PK profile of single or multiple oral doses of ABSK061 microt was assessed based on the primary pharmacokinetic parameters obtained.

Results of PK parameters and summary data will be provided for each participant. Descriptive statistics (arithmetic mean, standard deviation, coefficient of variation, median, minimum, maximum, geometric mean, and geometric coefficient of variation) were calculated for all PK parameters of oral ABSK061 in each treatment group except for tmax, which will be summarized as median, minimum, and maximum. Data listings for all PK parameters will be provided.

Part III assessed the effect of coadministration with soft food on the PK profile of ABSK061. The main PK parameters (Cmax, AUC0- ∞ , AUClast) were log-transformed and statistically analyzed using a linear mixed-effects model. The dosing sequence and period in the model served as fixed effects and participants (in sequence) served as random effects. The magnitude of the difference between the Least Squares Means (and their 90% confidence intervals and the Ratio of the Geometric Least Squares Means (RGLSM, taken with soft food/water) and their 90% confidence intervals were estimated by logarithmic transformation, and the intra-individual coefficient of variation was calculated for each parameter.

In addition, the dose-exposure proportionality of ABSK061 microchips was explored by graphical presentation of different doses by primary PK parameters (Cmax, AUC0- ∞ , AUClast) and/or dose-normalized primary PK parameters for each treatment group. If applicable, the dose-exposure proportionality will be further explored through the Power model by natural log-transformation of the primary PK parameters.

The detailed analysis plan will be further described in the Statistical Analysis Plan (SAP).

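### Table 10's per-participant effective half-life has no value when ARAUC is 1 or less, so its planned summary covers only participants above 1; how many drop out depends on half-life and accumulation figures the protocol leaves unreconciled

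*Protocol*

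**What the plan says.** Section 8.1.4 calculates PK parameters participant by participant and introduces Table 10 with "The following PK parameters will be reported". Among the multiple-dose rows, ARAUC is the steady-state AUCtau divided by the single-dose AUCtau, and the effective half-life is "eff = Ln (2) * tau/Ln ((AR/(AR-1))), where AR is ARAUC". No condition ARAUC > 1 is attached. Section 9.3.5 states that descriptive statistics, including arithmetic and geometric means, "were calculated for all PK parameters of oral ABSK061 in each treatment group except for tmax".

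The protocol gives several figures for how large the ratio will be:

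- Section 1.3, from the oncology study: "the mean terminal t1/2 values for each dose group ranged from 2.9 to 6.8 hours", and no marked accumulation, "with mean accumulation ratios of 1.2 to 2.2 for AUC across dose groups following QD or BID dosing". The intensively sampled groups listed there are seven BID groups and one QD group.
- Section 4.2: "Based on the half-life (median 5.4 h in adult oncology patients) and dosing frequency (QD) of the study drug", from which it concludes that "it can be stable after approximately 3.3 consecutive days of dosing, so it is proposed to test steady-state PK after 4 consecutive days".
- Section 4.3 reasons from an accumulation index of about 2.

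The only within-participant CV is in section 9.1, for the Part III precision table. It "was estimated as 70% of the above-mentioned weighted mean, I.e. 27.272%, 27.384%, 21.966"% for AUC0-∞, AUClast and Cmax. None is given for a Day 4/Day 1 AUCtau ratio.

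**The concern.** At ARAUC = 1 the formula divides by zero. Between 0 and 1 it takes the logarithm of a negative number. A drug with a short half-life given once daily has a true ratio just above 1, so ordinary within-participant variation will push some observed ratios to 1 or below. Those participants have no effective half-life. The ones who remain are partly those whose error raised the ratio, so a mean over them is a mean over a selected subset and can overstate the effective half-life.

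Each Part II sequence has 6 participants, so losing one or two matters for the summary. A reader could take an inflated mean as a sign of accumulation that is not there. Whether this is a real risk or a rare nuisance depends on the true ratio, and the protocol's own figures place that ratio anywhere from about 1.05 to about 2.

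**Working it through.** **1. The CV and the plan's own table.** With s = √ln(1 + CV²) and a 90% half-width of t(0.95; 2n − 4) × s × √(2/n), CV 27.272% gives s = 0.268. At n = 12 the half-width is 1.725 × 0.268 × √(2/12) = 0.189 and the interval is 0.828 to 1.208, as printed for AUC0-∞ in section 9.1. The 27.272% is therefore the within-participant CV the protocol itself works with. It is borrowed here for AUCtau, and 10% is shown as an assumed lower value.

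**2. Ratio implied by the half-life.** Under linear first-order kinetics, AR = 1/(1 − 2^(−tau/t½)).

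| Half-life | QD (24 h) | BID (12 h) |
|---|---|---|
| 2.9 h | 1.003 | 1.060 |
| 5.4 h | 1.048 | 1.273 |
| 6.8 h | 1.095 | 1.417 |

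No QD value reaches 1.2, the lowest mean reported, and no BID value reaches 2.

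**3. What an index of 2 implies.** Table 10's formula at AR = 2 gives ln2 × 24/ln2 = 24 h if the index is a QD value and 12 h if it is BID. An effective half-life of 12 h corresponds to a QD ratio of 1/(1 − (1 − 1/2)²) = 1.33.

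**4. Share undefined.** With independent log-normal error on Day 1 and Day 4, the SD of ln ARAUC is s√2, which is 0.379 at CV 27.272% and 0.141 at CV 10%. Then P(ARAUC ≤ 1) = Φ(−ln AR/(s√2)). For AR 1.048 and CV 27.272% this is Φ(−0.047/0.379) = Φ(−0.124) = 0.451.

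**5. Summary of the rest.** Table 10's formula was applied to 2,000,000 simulated ratios per case, keeping those above 1. The ratio in brackets compares the geometric mean with the effective half-life implied by the true AR.

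| True QD ratio | Implied t½,eff | Undefined, CV 27.3% | Geometric mean of rest | Undefined, CV 10% | Geometric mean of rest |
|---|---|---|---|---|---|
| 1.05 (5.4 h, section 4.2) | 5.4 h | 45% | 11.4 h (2.1×) | 37% | 7.2 h (1.3×) |
| 1.33 (index 2 read as BID) | 12 h | 22% | 14.4 h (1.2×) | 2% | 11.7 h (0.97×) |
| 2 (index 2 read as QD) | 24 h | 3% | 23.6 h (0.98×) | under 0.1% | 23.8 h (0.99×) |

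At AR 1.05 and CV 27.3%, a sequence of 6 expects 6 × 0.451 = 2.7 undefined values, and the chance of at least one is 1 − 0.549⁶ = 97%. At a QD ratio of 2 that chance is 19%.

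**6. The 3.3 days.** Reaching 90% of steady state takes log₂10 = 3.32 half-lives. At 5.4 h that is 3.32 × 5.4 = 17.9 h, or 0.75 days. It equals 3.3 days only for a half-life of about 24 h (3.32 × 24 = 79.7 h). The figure may also be a count of half-lives printed as days.

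**7. Group-level alternative.** With 6 participants the SD of the mean ln ARAUC is 0.379/√6. At AR 1.05 the group geometric mean is itself 1 or less with probability Φ(−0.047/0.155) = 38%, or 21% at CV 10%.

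**The case against.** The strongest reply is that rules for non-calculable PK values belong in the SAP, which is not shown and may contain one. That is a fair limit: a missing handling rule is not the finding. But the protocol itself fixes the formula, the participant level and the means to be taken, and within those choices the summary can only cover participants above 1.

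A reader might infer that nearly half of Part II will have no effective half-life and that the remainder will be overstated twofold. The documents do not support that as an expectation. It needs both the 1.05 ratio and a 27.3% CV, and that CV is 70% of a between-patient value planned for another part. The ratio of 1.05 is also a prediction from terminal half-life, whereas section 1.3 reports observed mean ratios of 1.2 to 2.2. Effective half-life is used because accumulation need not follow terminal half-life. Section 1.2 describes a drug cleared mainly by CYP3A4 that also moderately inhibits it, so accumulation above the linear prediction is possible, though not shown.

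A reader might also take the 3.3-day error to mean that Day 4 is too early or the washout too short. It does not: at 5.4 h, steady state comes well before Day 4.

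Finally, the parameter appears in no objective, endpoint list or escalation rule. That stands, and it limits the weight of the point.

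**Conclusion.** The point holds as a minor defect. Table 10 fixes a per-participant quantity that does not exist at ARAUC ≤ 1, and section 9.3.5 has it averaged, so the summary is restricted to ratios above 1. The scenarios run from about 45% undefined with a geometric mean 2.1 times the implied value (AR 1.05, CV 27.3%) to about 3% or less with no material bias (AR 2 under QD). The intermediate BID reading gives 22% or 2%, depending on the CV. These figures assume linear kinetics, independent log-normal error on the two days, and a CV the protocol does not supply for this ratio.

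Two conclusions need no CV. The formula is undefined at 1 or less, and the 3.3 days in section 4.2 does not follow from a 5.4 h half-life. Under linear kinetics, 5.4 h with QD dosing also does not match an index of about 2. ARAUC itself, Day 4 sampling, the washout and the 48 h last sample are not in question.

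**What to change.** In Table 10, make ARAUC with its 90% confidence interval per dose group the accumulation result. Derive the effective half-life only by transforming the dose-group geometric mean ARAUC and its confidence limits, printing *not estimable* wherever the value is 1 or less. List individual effective half-lives with the number of participants whose ARAUC is 1 or less, but do not average them, and exempt this row from the summary rule in section 9.3.5.

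In sections 4.2 and 4.3, correct or source the 3.3-day figure, and reconcile the half-life and accumulation statements there with those in section 1.3, saying whether the index of about 2 refers to QD or BID dosing.

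The cost is one table row, its summary rule and some wording. No dose, schedule, sampling or sample-size change is involved. The drawback is that the group value may itself be not estimable (38% or 21% in the least favourable scenario above), but it uses all participants and shows the limitation openly.
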